### Analysis Populations

Intent-to-Treat (ITT): Subjects randomized into the study.

Safety: ITT subjects who insert at least 1 tampon

Modified Intent-to-Treat (MITT): Safety subject who returns at least 1 tampon that can be assessed for elongation.

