### Key Secondary Endpoints

Diary responses will be used to assess the following user needs:

- Product to remain clean prior to use
- Product to remain in working condition prior to use
- User can access the product
- User can vaginally insert and place the tampon
- User can remove product from the vagina after use
- Product absorbs fluid

Analysis will be done separately for each absorbency using the Safety population.

Interview responses will be used to assess the following user needs:

- User is able to distinguish between absorbency levels
- Packaging is labeled properly

Interview responses will only be done for both absorbencies combined for the ITT population.

Product tolerability will be evaluated through the following measures:

- Gynecological exam findings
- Frequency and severity of adverse events

Analysis will be done separately for each absorbency using the Safety population.

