### **Validation Criteria**

The primary objective of this study is to validate that changes in the design of the [REDACTED] tampons meet defined user needs. The primary objective will have been met if the following criteria are met:

- Test tampon elongation rate is the same as or better than the reference tampon for each absorbency, where same is defined as test tampon elongation rate  $\leq$  reference tampon elongation rate .
- Product tolerability is deemed to be acceptable based on review of the results.
- Diary responses have  $\geq 96\%$  response rates consistent with each user need for each absorbency. If the rate is lower than 96%, the response rate consistent with the user need related to the test tampon must be the same as or better than the response rate of the reference tampon, where same is defined as test tampon response rate  $\geq$  reference tampon response rate.
- Interview responses demonstrate that 95% of users are able to identify key information on the package and insert, and able to distinguish between absorbency levels on the wrappers.

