4.2. Interim Analysis and Data Monitoring

No interim analyses are planned.

5. Analysis Populations

The following analysis populations are planned for this study:

- **Intent-To-Treat Population (ITT):** The ITT population includes all subjects randomized into the study.
- **Safety Population:** The Safety Population includes all ITT subjects who insert at least 1 tampon.
- **Modified Intent-To-Treat Population (MITT):** The MITT population includes all safety subjects who have no major protocol deviations and return at least 1 tampon that can be assessed for elongation.

Assignment of subjects to populations will be determined at a data review meeting prior to database lock.

6. General Issues for Statistical Analysis

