8.2. Diary Responses

The number and percentage of diary responses will be reported for test tampon diary entries and reference tampon diary entries in the Safety population, and separately for each absorbency arm. Diary responses for individual tampon entries will be summarized separately from diary responses following last tampon use. Diary responses for individual tampon entries were reported specific to each tampon used and were recorded repeatedly for each used tampon throughout a given menstrual cycle. The denominator for the percentage calculation for individual tampon entry diary responses will be based upon the total number of used tampon diary entries within each question and within each test article type and within each absorbency arm. The number of tampons remaining white and when the subject reported having any flow when using the tampon will be summarized within each test article type and within each absorbency arm as well. The denominator for the percentage calculation will be the total number of used tampon diary entries within each question and within each test article type and within each absorbency arm. Diary responses recorded following last tampon use were reported only once per menstrual cycle. The reasons for not inserting the tampon using the applicator will be summarized. The denominator for the percentage calculation for diary responses following last tampon use will be based on the total number of diary entries within each question and within each test article type and within each absorbency arm. Individual diary responses and diary responses recorded following the last tampon will be listed. And additionally, the reasons for not inserting the tampon using the applicator will be presented in a separate listing. The 95% CIs for the percentage of patients who are able to insert each tampon will be computed using the exact method (Clopper & Pearson, 1934).

In addition, the testing of equality of proportions of patients who are able to insert each tampon between test and reference article types within each absorbency arm will be performed. For this purpose, the difference between proportions will be calculated along with 95% Wald CIs. Pearson chi-square test will be computed in support of hypothesis testing. The samples for comparison will be considered independent.

The following hypothesis will be tested:

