Note: Percentages are n/Number of used tampon diary entries recorded by subjects in the Safety Population within each question and within tampon type*100. Subject diaries were returned at the post-use visits which were conducted within 72 hours following the last tampon use for that menstrual cycle. Diary responses for individual tampon entries were reported specific to each tampon used and were recorded repeatedly for each used tampon throughout a given menstrual cycle. Subjects used each test article type (reference or test tampon) over the course of one menstrual cycle.

*Subjects must have reported both the whole product remained white and reported anything other than "No flow". Percentages are n/Number of used tampon diary entries recorded by subjects in the Safety Population that indicate anything other than "No Flow" within tampon type*100.

n is the total number of diary entries for each section of the table. N is the number of subjects within each article and within absorbency arm.

Reference Listing: 16.2.6.2.1

Programming Note: Repeat for Absorbency Arm: Super.

[figure not shown]

Table 14.2.2.2
 Summary of Diary Responses Following Last Tampon Use
 Safety Population

Absorbency Arm: Regular	Test Tampon (N=XX)	Reference Tampon (N=XX)
Variable Category		
Able to open the box to retrieve wrapped tampons	XX	XX
Yes	XX (XX.X%)	XX (XX.X%)
No	XX (XX.X%)	XX (XX.X%)
Able to open each tampon wrapper	XX	XX
Yes	XX (XX.X%)	XX (XX.X%)
No	XX (XX.X%)	XX (XX.X%)
Tampons were clean prior to use	XX	XX
Yes	XX (XX.X%)	XX (XX.X%)
No	XX (XX.X%)	XX (XX.X%)
Able to insert each tampon using the applicator	XX	XX
Yes	XX (XX.X%)	XX (XX.X%)
No	XX (XX.X%)	XX (XX.X%)
Percentage of patients who are able to insert each tampon using the applicator	XX.XX%	XX.XX%
95% CI for the Percentage [1]	XX.XXX%, XX.XXX%	XX.XXX%, XX.XXX%
Difference in Percentage	XX.XX%	
95% CI for the Difference in Percentage [1]	XX.XXX%, XX.XXX%	
Chi-Square	XX.X	
P-Value	X.XXX	
Able to insert each tampon using the applicator (diary #1)	XX	XX
Yes	XX (XX.X%)	XX (XX.X%)
No	XX (XX.X%)	XX (XX.X%)
Able to insert each tampon using the applicator (diary #2)	XX	XX
Yes	XX (XX.X%)	XX (XX.X%)
No	XX (XX.X%)	XX (XX.X%)
Reason why was not able to insert tampon using the applicator	XX	XX
Not able to fully extend the applicator	XX (XX.X%)	XX (XX.X%)
Too hard to push the tampon out of the applicator	XX (XX.X%)	XX (XX.X%)

No tampon in the applicator	XX (XX.X%)	XX (XX.X%)
Applicator was damaged	XX (XX.X%)	XX (XX.X%)

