Note: Study day is calculated relative to the date of first insertion of study product (either test or reference tampon).

Programming Note: If "Deviation Occurred During a Time Frame?" is "No" then repeat Deviation Start Date (Study) for Deviation End Date (Study Day) and repeat First Visit Impacted for Last Visit Impacted. If there is text for "Additional Description (Other than "NA", "N/A" and similar)", then concatenate that text with the text for "Description", e.g., "DESCRIPTION TEXT XXX. ADDITIONAL TEXT." Repeat for Absorbency Arm: Regular and Absorbency Arm: Super.

Listing 16.2.2.3
Reason for Screen Failures
Screen Failures

Subject ID	Failed Date	Met All Eligibility Criteria?	Criteria Not Met/Reason Not Met
XXXXX	DDMMYYYYYY	No	Inclusion #4/XXXXXXXXXXXXXXXXXXXX; Exclusion #2/XXXXXXXXXXXXXX
XXXXX	DDMMYYYYYY	No	Inclusion #1/XXXXXXXXXXXXXXXXXXXX; Exclusion #9/XXXXXXXXXXXXXX
XXXXX	DDMMYYYYYY	No	Inclusion #8/XXXXXXXXXXXXXXXXXXXX; Exclusion #5/XXXXXXXXXXXXXX
XXXXX	DDMMYYYYYY	No	Inclusion #6/XXXXXXXXXXXXXXXXXXXX; Exclusion #12/XXXXXXXXXXXXXX

Programming Note: If there is no "Reason Not Met" included for the corresponding criteria not met, then concatenate the criteria not met with "Reason not given", e.g., "Inclusion #1/Reason not given". If there are multiple criteria met, please list each criteria/reason not met concatenated with a ";".

Listing 16.2.3.1
Analysis Populations
All Subjects

Absorbency Arm: XXX

Subject ID	Date	Number	Randomization		Analysis Populations				Primary Reason(s) for Exclusion
			Tampon Used	Part of Subset? [1]	ITT [2]	Safety [3]	MITT [4]		
XXXXXX	DDMMYY	XXXX	XXXXXXXX	XXXXXXXX	Yes	No	No	Safety: Subject did not insert any tampons.	
XXXXXX	DDMMYY	XXXX	XXXX	XXXX	Yes	Yes	Yes		
XXXXXX	DDMMYY	XXXX	XXXXXXXX	XXXXXXXX	Yes	Yes	No	MITT: Subject did not return any tampons that could be assessed for elongation.	
XXXXXX	DDMMYY	XXXX	XXXX	XXXXXX	No	No	No	ITT: Subject was not randomized.	

Abbreviations: BR = regular absorbency test tampon; BS = super absorbency test tampon; CR = regular absorbency reference tampon; CS = super absorbency reference tampon; ITT = intent-to-treat; MITT = modified intent-to-treat.

[1] A subset of subjects were selected to undergo gynecological exams prior to and following tampon use. In addition, this subset of subjects completed the packaging and labeling interview at the Screening/Baseline Visit (Visit 1).

[2] The ITT Population includes all subjects randomized into the study.

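### Women who never insert a tampon drop out of the insertion and access rates, even when their diary records the failure

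*SAP*

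**What the plan says.** Protocol section 11 lists the user needs to be scored from the diary, among them access to the product and vaginal insertion, and then states: "Analysis will be done separately for each absorbency using the Safety population". SAP 8.2 makes the same choice: "The number and percentage of diary responses will be reported for test tampon diary entries and reference tampon diary entries in the Safety population".

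Protocol section 11 defines the population as "Safety: ITT subjects who insert at least 1 tampon". SAP section 5 reads "The Safety Population includes all ITT subjects who insert at least 1 tampon", whereas for ITT it reads "The ITT population includes all subjects randomized into the study". The sample text in Listing 16.2.3.1 shows the exclusion at work: "Safety: Subject did not insert any tampons".

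The access and insertion items are answered once per cycle, after the last tampon. Table 14.2.2.2 (Safety population) has rows for opening the box, opening each wrapper, cleanliness and "Able to insert each tampon using the applicator". Under SAP 8.2 the denominator is the number of recorded entries per question, product and absorbency.

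The diary criterion is one of the conditions for meeting the primary objective (Protocol section 11, Validation Criteria; SAP 2.1.1). It asks for 96% on each user need in each absorbency, with a fallback: "If the rate is lower than 96%, the response rate consistent with the user need related to the test tampon must be the same". The comparison is with the reference tampon, whose rate the test tampon has to equal or exceed.

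**The concern.** Membership of the analysis set depends on the outcome being measured. A woman who could not open or insert anything is the clearest failure of these two user needs, and she is the one the population rule takes out. Such failures are foreseen: Table 14.2.2.2 has rows for a tampon that is too hard to push out, a damaged applicator and an empty applicator.

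The exclusion also depends on randomized order. Complete failure with the first product followed by withdrawal removes the woman. Complete failure with the second product does not, because she has already qualified with the first.

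Her answers then appear in no planned output. The diary listings (16.2.6.2.1 to 16.2.6.2.3) are limited to the Safety population, although SAP 6.1.5 says that all collected data will be listed. The exact confidence intervals and the chi-square test for insertion in SAP 8.2 use the same set. So do the adverse event summary tables.

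**Working it through.** **Inputs.** 369 women per absorbency (Protocol section 11; SAP 3.2); the 96% threshold and its fallback; the Safety definition above. The documents do not say how many women will insert nothing, so that number is assumed.

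**The plan's own figure.** With elongation rates of 0.7% and 0.2%, two-sided alpha 0.05 and 80% power, the arcsine formula n = 2(z₀.₉₇₅ + z₀.₈₀)²/h², where h = 2·asin√0.007 − 2·asin√0.002, gives 2,577 tampons per type. At 7 usable tampons per woman, 2,577/7 = 368.1, rounded up to 369. This reproduces the stated size. It concerns elongation and only supplies the denominator used below.

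**Who is counted.** Safety membership is tied to neither product nor cycle.

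| Pattern | In Safety? | Recorded No counted? |
|---|---|---|
| Fails with some tampons of a product | Yes | Yes |
| Inserts first product, none of the second | Yes | Yes |
| Inserts none of the first, then at least one of the second | Yes | Yes |
| Inserts none of the first, then withdraws | No | No |
| Inserts none of either product | No | No |

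Only the last two rows are lost. Partial failures score No because the item asks about every tampon.

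**Insertion item.** Let N women answer for a product, k of them be excluded with a recorded No, and f others answer No.

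- All recorded answers: (N − k − f)/N
- Safety population: (N − k − f)/(N − k)
- Difference: k(N − k − f)/[N(N − k)], which is never negative

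With N = 369 (everyone answers), 0.96 × 369 = 354.24. So 355 Yes answers are needed and at most 14 No answers are allowed (355/369 = 96.21%).

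| k (assumed) | f | All recorded answers | Safety |
|---|---|---|---|
| 1 | 14 | 354/369 = 95.93% | 354/368 = 96.20% |
| 5 | 14 | 350/369 = 94.85% | 350/364 = 96.15% |
| 5 | 10 | 354/369 = 95.93% | 354/364 = 97.25% |
| 5 | 0 | 364/369 = 98.64% | 364/364 = 100% |

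For k from 1 to 15, the 96% result changes only if there are at least 15 failures in total and no more than 14 of them are counted. The last row passes either way.

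**Access and cleanliness items.** A woman who opened everything but could not insert would answer Yes to access. With 14 No answers, dropping one such Yes moves 355/369 = 96.21% to 354/368 = 96.20%. The direction is not fixed for these items.

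**Fallback.** Exclusions after failure with the test product raise the test rate; exclusions after failure with the reference raise the reference rate. The net effect on the comparison depends on the balance between the two.

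**The case against.** The strongest reply is that this is a narrow edge case. Inclusion requires a history of applicator use without discomfort and normal use of at least six tampons per period (Protocol section 7). The modified product differs only in string placement (Protocol section 8), so nothing in the documents suggests that its applicator fails more often. Exclusions are visible: Table 14.1.1 gives ITT and Safety counts by arm, and Listing 16.2.3.1 gives each woman's reason. Changing the population alone may also achieve little, since the items are asked after last use and a woman with no use may have no entry. All of this stands, and it limits the size of the point. It does not remove the rule that discards a No that was recorded.

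A reader might infer more than the documents support:

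- *That every complete failure with the test tampon is removed.* It is removed only if the woman also inserts no reference tampon.
- *That entry to the set requires success on the endpoint.* Entry needs one insertion by any means; the item asks about every tampon using the applicator.
- *That the rule can only raise rates.* This holds for each product's insertion rate, but not for access or cleanliness, nor for the fallback comparison.
- *That one exclusion turns failure of the criterion into success.* Missing 96% does not fail it; the decision passes to the comparison with the reference.
- *That an injury during a failed attempt goes unreported.* Adverse events are collected from dispensation (Protocol section 12), and Listing 16.2.7.1 covers all subjects. The gap is in the summary tables.

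**Conclusion.** The point holds in a limited form and should be corrected. Women with no insertion in the whole study are left out of the insertion and access rates by a rule that selects on the outcome, even where a No is on record. For insertion this biases each product's rate upward, and inclusion of the same complete failure depends on the cycle in which it happens.

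The size is unknown. One exclusion is worth about 0.3 percentage points near the threshold (96.20% against 95.93%), and five are worth 1.3 points (96.15% against 94.85%). These figures assume that all 369 women answer and that k lies between 1 and 5, neither of which the documents establish. The number is probably small in experienced users, and a change of result at 96% needs at least 15 failures in all. The fallback offers no independent protection, because it is computed in the same filtered set.

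**What to change.** 1. In Protocol section 11, SAP 8.2 and Table 14.2.2.2, analyse the end-of-cycle items (box, wrapper, cleanliness, insertion) in all ITT women dispensed that product who have a recorded answer, whether or not any insertion succeeded.
2. For access and insertion only, also count as No a woman without an entry whose documented reason for non-use or discontinuation is inability to open or insert that product. Table 14.1.1 has no such category, so agree how free-text reasons are classified at the data review meeting before database lock.
3. Report the number of women with zero insertions by product, and extend the diary listings to them.
4. Keep the Safety population for the per-tampon removal and absorption items. Its definition can stay as it is, so MITT is untouched.
5. Show adverse events in dispensed women with no insertion in the summary tables as a separate group, since the period rule in SAP 9.1 needs a first insertion date.

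The cost is wording in Protocol section 11, SAP 8.2, Table 14.2.2.2 and the diary listings, plus one added group in the adverse event tables. The documents show no need for new data collection, provided reasons for non-use and discontinuation are recorded. The reported percentages may be slightly less favourable.

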2.1. Study Objective

2.1.1. Primary Objective

The primary objective of this study is to validate that changes in the design of the [REDACTED] tampons meet defined user needs. The primary objective will have been met if the following criteria are met:

- Test tampon elongation rate is the same as or better than the reference tampon for each absorbency, where same is defined as test tampon elongation rate \leq reference tampon elongation rate.
- Product tolerability is deemed to be acceptable based on review of the results.
- Diary responses have $\geq 96\%$ response rates consistent with each user need for each absorbency. If the rate is lower than 96%, the response rate consistent with the user need related to the test tampon must be the same as or better than the response rate of the reference tampon, where same is defined as test tampon response rate \geq reference tampon response rate.

- Interview responses demonstrate that 95% of users are able to identify key information on the package and insert, and able to distinguish between absorbency levels on the wrappers.

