Absorbency Arm: Regular	Variable Statistic	Test Tampon (N=XX)	Reference Tampon (N=XX)
Length of Elongation			
n [1]		XX	XX
Mean (SD)		XX.X (XX.XX)	XX.X (XX.XX)
Median		XX.X	XX.X
Min, Max		XX, XX	XX, XX
Elongated [2]			
n [1]		XX	XX
Percentage		XX.XX%	XX.XX%
95% CI for the Percentage [3]		XX.XXX%, XX.XXX%	XX.XXX%, XX.XXX%
Difference in Percentage		XX.XX%	
95% CI for the Difference in Percentage [4]		XX.XXX%, XX.XXX%	
Chi-Square		XX.X	
P-Value		X.XXX	

Abbreviations: CI = confidence interval; MITT = modified intent-to-treat; SD = standard deviation.

Note: Percentages are n/Number of used tampons returned by subjects in the MITT Population within tampon type*100. Length is measured in millimeters (mm). Tampon integrity assessments were performed at the post-use visits which were conducted within 72 hours following the last tampon use for that menstrual cycle. Subjects used each test article type (reference or test tampon) over the course of one menstrual cycle. N is the number of subjects within each article and within absorbency arm.

[1] n is the number of tampons.

[2] Any used tampon with a measurement of elongation >10 mm was considered elongated.

[3] The 95% CIs for the percentage elongated estimates were computed using the exact method.

[4] The 95% CIs for the difference in percentage elongated estimates were computed using Wald method

Reference Listing: 16.2.6.1

Programming Note: Repeat for Absorbency Arm: Super.

[figure not shown]

Table 14.2.2.1
 Summary of Individual Tampon Entry Diary Responses
 Safety Population

Absorbency Arm: Regular	Test Tampon (N=XX)	Reference Tampon (N=XX)
Variable Category		
Able to remove the tampon	XX	XX
Yes	XX (XX.X%)	XX (XX.X%)
No	XX (XX.X%)	XX (XX.X%)
White area remaining on tampon	XX	XX
No areas on the tampon remained white	XX (XX.X%)	XX (XX.X%)
Less than half of the tampon remained white	XX (XX.X%)	XX (XX.X%)
About half of the tampon remained white	XX (XX.X%)	XX (XX.X%)
More than half of the tampon remained white	XX (XX.X%)	XX (XX.X%)
Whole product remained white	XX (XX.X%)	XX (XX.X%)
Flow when using the tampon	XX	XX
No flow	XX (XX.X%)	XX (XX.X%)
Spotting only	XX (XX.X%)	XX (XX.X%)
Light	XX (XX.X%)	XX (XX.X%)
Medium	XX (XX.X%)	XX (XX.X%)
Heavy	XX (XX.X%)	XX (XX.X%)
Tampons remaining white and where subject reported having any flow when using the tampon*	XX (XX.X%)	XX (XX.X%)

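### SAP 8.2 and the Table 14.2.2.1 footnote use different denominators for tampons wholly white despite flow; if that row decides fluid absorption, the 96% criterion can be calculated in two ways

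*SAP*

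**What the plan says.** SAP 8.2 (Diary Responses) introduces one composite summary: "The number of tampons remaining white and when the subject reported having any flow when using the tampon will be summarized". The sentence after it sets the denominator: "The denominator for the percentage calculation will be the total number of used tampon diary entries within each question", by article type and absorbency arm. Nothing in it removes entries made when there was no flow.

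The shell of Table 14.2.2.1 (SAP 14.2) carries the same row, "Tampons remaining white and where subject reported having any flow when using the tampon", marked with a star. The starred footnote first defines the numerator: "Subjects must have reported both the whole product remained white and reported anything other than" no flow. It then gives the denominator: "Percentages are n/Number of used tampon diary entries recorded by subjects in the Safety Population that indicate anything other than" no flow. The table's general note has the same rule as 8.2: "Percentages are n/Number of used tampon diary entries recorded by subjects in the Safety Population within each question and within tampon" type. Within the shell, therefore, the star is an explicit exception to the general note. The conflict lies between the text of 8.2 and the shell.

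SAP 2.1.1 and the Validation Criteria in protocol section 11 require at least 96% of diary responses to be consistent with each user need, for each absorbency. There is a fallback: "If the rate is lower than 96%, the response rate consistent with the user need related to the test tampon" must be at least that of the reference. SAP 2.2.1.2 lists fluid absorption among the needs assessed by diary, but no section names the diary row that decides it.

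**The concern.** The two rules give different percentages for the same row whenever any entry reports no flow, and the table has a category for that response. An entry with no flow can never be wholly white despite flow. Keeping it in the denominator dilutes the failure percentage by the factor (1 − no-flow share).

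This row is the natural measure of fluid absorption because it is the only diary row that combines whiteness with flow. If it is the measure, the 8.2 rule can pass the test tampon on the absolute 96% line where the footnote rule would send it to the comparison with the reference. When the no-flow share is the same for both products, the comparison itself is unaffected and only its trigger moves. When the shares differ, the comparison can reverse as well.

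Another reading is possible: the need could be judged on the category "Whole product remained white" in the white-area row. On that reading the criterion is untouched and only the reported percentage is in conflict.

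**Working it through.** **Inputs from the documents.** Protocol section 11 assumes 369 subjects per absorbency and 7 used tampons per cycle: 369 × 7 = 2,583 per tampon type, which is half of the stated 5,166. SAP 3.2 prints 2,538 per type, which does not fit 5,166; 2,583 is used here. It stands in for the number of diary entries per product, N. The threshold is 96%, so at most 4% may fail.

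**Assumptions, not in the documents.** No-flow share f of 5 to 30%. True failure rate q among flow entries, examined from 1 to 6%. Independent entries, with the same f and q for both products.

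**Step 1: the two rates.** Let w be the number of entries wholly white despite flow, and m = N(1 − f), rounded, the number of flow entries.

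- SAP 8.2: consistent rate = 1 − w/N. It passes if w ≤ 0.04 × 2,583 = 103.3, so up to 103.
- Footnote: consistent rate = 1 − w/m. It passes if w ≤ 0.04m.

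| f | m | Largest w passing, 8.2 | Largest w passing, footnote | Rules disagree for w | Failure share among flow entries tolerated by 8.2 (103/m) | Rate at w = 103, 8.2 / footnote |
|---|---|---|---|---|---|---|
| 5% | 2,454 | 103 | 98 | 99–103 | 4.20% | 96.01 / 95.80% |
| 10% | 2,325 | 103 | 93 | 94–103 | 4.43% | 96.01 / 95.57% |
| 20% | 2,066 | 103 | 82 | 83–103 | 4.99% | 96.01 / 95.01% |
| 30% | 1,808 | 103 | 72 | 73–103 | 5.70% | 96.01 / 94.30% |

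**Step 2: chance of passing, with the fallback.** Let c be the cut-off from the table, and let X_test and X_ref be independent Binomial(m, q). Then

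P(pass) = P(X_test ≤ c) + Σ over x > c of P(X_test = x) × P(X_ref ≥ x).

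Results, 8.2 rule / footnote rule:

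| q | f = 5% | f = 10% | f = 20% | f = 30% |
|---|---|---|---|---|
| 1% and 2% | 100 / 100% | 100 / 100% | 100 / 100% | 100 / 100% |
| 3.5% | 97 / 92% | 99 / 92% | 100 / 89% | 100 / 89% |
| 4% | 76 / 64% | 88 / 65% | 99 / 63% | 100 / 64% |
| 5% | 51 / 51% | 52 / 51% | 64 / 51% | 92 / 52% |
| 6% | 51 / 51% | 51 / 51% | 51 / 51% | 56 / 51% |

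The gap is at least 5 percentage points only for q of about 3.5–4.3% (f = 5%), 3.5–4.6% (f = 10%), 3.4–5.2% (f = 20%) or 3.4–6.0% (f = 30%). The largest gaps are 12, 23, 40 and 47 points respectively. At f = 2% the largest gap is 4.8 points.

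**Step 3: unequal no-flow shares.** Take an assumed example with 2,583 entries per product: 118 test failures with 15% no flow (m = 2,196), and 120 reference failures with 5% no flow (m = 2,454).

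- All entries: test 1 − 118/2,583 = 95.43%, reference 1 − 120/2,583 = 95.35%. Test passes the fallback.
- Flow entries only: test 1 − 118/2,196 = 94.63%, reference 1 − 120/2,454 = 95.11%. Test fails it.

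**The case against.** The strongest reply is that the shell already gives a working rule. The footnote is attached to this row, states both numerator and denominator, and departs openly from the general note. The 8.2 sentence may be standard wording that was not updated, and a programmer would probably follow the footnote. That is plausible, but nothing in the SAP says the shell prevails over the text. Nor can the phrase about each question be read as the flow-only set: 8.2 and the table's general note use it elsewhere for all entries answering a question.

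The link to the 96% criterion rests on a mapping that no document states. This stands, and the missing mapping is a gap in its own right. The criterion itself also defines no denominator. Flow entries are the sensible base, because a tampon used without flow cannot show absorption, but the criterion does not say so.

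The size depends on assumed inputs. Nothing in the documents suggests that 4% of tampons stay wholly white despite flow, and at 1–2% the choice has no effect on passing. The 2,583 figure comes from tampons usable for the elongation analysis, whereas the diary rows use the Safety population. The model also ignores clustering of about seven entries per woman and the pairing of products in a crossover. All of this limits the probabilities to illustrations; the cut-offs in Step 1 need only N and f.

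Finally, the table prints the flow categories by product, so a reader can convert one percentage to the other. That loses no information, but it does not say which figure is held against 96%.

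**Conclusion.** The concern holds. SAP 8.2 and its own table give different percentages for the same row, and the 8.2 rule counts entries that cannot fail as successes. That much depends on no assumption beyond some entries reporting no flow.

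The effect on the validation decision is conditional. It requires that this row decides fluid absorption and that the failure rate among flow entries lies near the 4% line. With 2,583 entries and a no-flow share of 5 to 30%, the 8.2 rule tolerates about 4.2 to 5.7% failures among flow entries instead of 4%. Near the line, under the independence model, this can move the chance of passing by 12 to 47 points at most. Outside that window the choice hardly changes the result, unless the no-flow share differs between products, when the fallback comparison may also change direction. This should be corrected before the data are analysed; it does not undermine the study.

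**What to change.** In SAP 8.2, replace the denominator sentence for this row so that the base is diary entries reporting any flow, by product and absorbency, as the Table 14.2.2.1 footnote already has it. State that this denominator applies both to the 96% check and to the comparison of test with reference.

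Add one sentence saying whether the complement of this row is the measure of fluid absorption; if it is not, name the row that is.

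The cost is one replaced sentence and one or two added ones in SAP 8.2. No new data are needed and the table footnote stays as it is.
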